11.4 STATISTICAL METHODS

11.4.1 Extent of study treatment exposure and compliance

The extent of study treatment exposure and compliance will be assessed separately for Part 1 and Part 2 of the study, and summarized by actual treatment received within the Part 1 safety population and Part 2 safety population respectively.

Within each part of the study, duration of IMP exposure is defined as: last dose date - first dose date +1 day, regardless of unplanned intermittent discontinuations.

11.4.2 Analyses of efficacy endpoints

All analyses of efficacy endpoints will be done on Part 2 of the study and will not include patients from Part 1 who are rerandomized in Part 2. Efficacy data in patients from Part 1 will be described separately, with no formal statistical testing.

11.4.2.1 Analysis of primary efficacy endpoint

The primary efficacy endpoint is the change from baseline to Week 52 in MDS-UPDRS Part II+III score.

The primary analysis will be based on an ITT approach, including all data regardless of adherence to treatment and protocol. Change from baseline in MDS-UPDRS Part II+III score will be analyzed using a mixed effect model with repeated measures (MMRM). All postbaseline data

available within Week 13 to Week 52 analysis windows will be used and missing data will be accounted for by the MMRM model. The model will include the fixed categorical effects of treatment group (GZ/SAR402671 versus placebo), randomization strata, time point (Week 13, Week 26, Week 39, and Week 52), treatment-by-time point interaction as well as the continuous fixed covariates of baseline MDS-UPDRS Part II+III score. This model will provide baseline adjusted least squares means estimates at Week 52 for both treatment groups with their corresponding standard errors and 95% confidence intervals (CI). To compare the GZ/SAR402671 group to the placebo group, an appropriate contrast statement will be used to test the differences of these estimates, at the 2-sided 0.05 level.

The MMRM model relies on the “missing-at-random” (MAR) assumption. As the possibility for a not-missing-at-random (NMAR) missingness mechanism cannot be excluded, a sensitivity analysis to explore the impact of nonignorable missingness on the primary efficacy analysis will be conducted.

The sensitivity analysis will use a control-based pattern-mixture model (PMM) method. This PMM method will make the assumption that, in case of missing data after permanent treatment discontinuation, the MDS-UPDRS Part II+III scores for patients in the GZ/SAR402671 arm will follow the same trajectory as for patients in the placebo arm. As a consequence, missing data after permanent treatment discontinuation will be imputed using a model estimated solely from data observed in the placebo arm. Missing data during the treatment period will be imputed separately assuming MAR, using a model estimated from data observed during the treatment period within the same treatment arm. Missing values will be imputed 100 times to generate 100 complete data sets. Each completed dataset will be analyzed using an analysis of covariance (ANCOVA) of change from baseline to Week 52 in MDS-UPDRS Part II+III score, including the fixed categorical effects of treatment group (GZ/SAR402671 versus placebo), randomization strata, as well as the continuous fixed covariates of baseline value. The final results will be obtained by combining the least squares means and least squares mean differences from these 100 analyses, using Rubin’s formula.

The primary analysis will be repeated using a PP approach. Movement Disorder Society-Unified Parkinson’s Disease Rating Scale data collected after a major protocol deviation that potentially impacts the primary efficacy endpoint will be excluded from this analysis. The criteria for exclusion of data will be determined and documented prior to database lock. The PP analysis will be used for sensitivity analysis purposes.

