11.1 DETERMINATION OF SAMPLE SIZE

Part 1: Dose Escalation Phase

As Part 1 is an exploratory, dose-escalation study, the sample size is not based on the statistical power calculation. Each cohort (for non-Japanese patients only) will have a 4:1 randomization ratio, and the total sample size will be approximately 15 patients (including 12 on GZ/SAR402671 and 3 on placebo).

For Japanese patients only, each cohort will have a 3:1 randomization ratio, and the total sample size will be approximately 12 Japanese patients (including 9 on GZ/SAR402671 and 3 on placebo). This sample size in Japanese Part 1 is considered based upon empirical and feasibility considerations.

Therefore, the total sample size in Part 1 will be approximately 27 patients.

Patients who do not complete a minimum number of scheduled doses of study drug in Part 1 and withdraw for reasons other than safety may be replaced.

Part 2: Treatment Phase

Approximately 216 PD patients carrying a GBA mutation in total will be randomized in a 1:1 ratio to the GZ/SAR402671 or placebo groups. A sample size of 108 patients for the GZ/SAR402671 group and 108 for the placebo group provides at least 80% power to detect a 4.06 points improvement compared to the placebo mean change in MDS-UPDRS Parts II+III score over 52 weeks. This sample size calculation assumes a 2-sided alpha = 0.05, a standard deviation for the change from baseline to Week 52 in MDS-UPDRS Part II+III of 10.01 points (estimated from the Parkinson's Progression Markers Initiative [PPMI] database), and allows for an approximate 10% early terminations/unevaluable patients.

A previous study showed that a 3.25 points difference on MDS-UPDRS Part III represent the minimal clinically important difference (MCID) for detecting an improvement. It was estimated from the PPMI database that the standard deviation for change from baseline to Week 52 in MDS-UPDRS Part III was 8.01 points; therefore, the MCID of 3.25 points would represent an effect size of 0.406. Since no study evaluated the MCID for MDS-UPDRS Part II+III, the same effect size of 0.406 was assumed, resulting in an estimated MCID of 4.06 points, using the standard

deviation of 10.01 for change from baseline to Week 52 in MDS-UPDRS Part II+III also estimated from the PPMI database.

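### The primary MMRM fits one baseline slope for all four visits; a baseline-by-time point term is a near-free safeguard for precision at Week 52

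*Protocol*

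**What the plan says.** Section 11.4.2.1 builds the primary MMRM from treatment group, the stratification factors and these time terms: "time point (Week 13, Week 26, Week 39, and Week 52), treatment-by-time point interaction". Baseline is then entered as a main effect only, in the words "as well as the continuous fixed covariates of baseline MDS-UPDRS Part II+III score". No baseline-by-time point term appears. The tested comparison is at the last visit only: "This model will provide baseline adjusted least squares means estimates at Week 52 for both treatment groups".

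The control-based sensitivity analysis in the same section fits an ANCOVA of the Week 52 change to each imputed data set, with baseline as covariate. Section 11.4.2.2 carries the primary MMRM over to the three secondary endpoints.

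The sample size in 11.1 rests on "a standard deviation for the change from baseline to Week 52 in MDS-UPDRS Part II+III of 10.01 points". "A sample size of 108 patients for the GZ/SAR402671 group and 108 for the placebo group" is said to give the planned power (it "provides at least 80% power to detect a 4.06 points improvement compared to the placebo mean change"), and the plan "allows for an approximate 10% early terminations/unevaluable patients".

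**The concern.** A single slope is the right adjustment at Week 52 only if change depends on baseline in the same way at every visit. If it does not, the fitted slope is a weighted average over the four visits. The mismatch at Week 52 then goes into the residual and widens the standard error of the only contrast that is tested. The secondary endpoints inherit the same model.

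There is also a question of comparability. The sensitivity ANCOVA is fitted at Week 52 alone, so its baseline slope is specific to that visit. The MMRM slope is pooled. If slopes differ by visit, a gap between the two results would partly reflect baseline adjustment, although the sensitivity analysis is meant to probe missing data.

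**Working it through.** **1. The plan's own figure (inputs from 11.1).** Two-sided alpha 0.05, 80% power, difference 4.06, SD 10.01.

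- Normal approximation: n per arm = 2 × (1.960 + 0.842)² × (10.01/4.06)² = 95.4, so 96. The t-test gives 97.
- Allowance for 10% loss: 97/0.9 = 107.8, so 108 per arm. The stated figure reproduces.
- Power at 97 evaluable per arm is 80.6% (normal) or 80.2% (t). The SD of 10.01 is not adjusted for baseline, so the plan counts on no gain from the covariate.

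**2. What a common slope does.** Let b be the true baseline slopes at the four visits and S the residual covariance, taken as unstructured. The fitted common slope tends to b* = (1'S⁻¹b)/(1'S⁻¹1). The relative excess variance at Week 52, against a model with visit-specific slopes, is

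(b52 − b*)² × Var(baseline) / residual variance at Week 52.

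**3. Assumptions.** The protocol gives no baseline SD, visit slopes or within-patient correlations. I took baseline SD 10, 13 or 16; SD of change rising from 8.0 at Week 13 to 10.01 at Week 52; slopes drifting linearly; and two levels of within-patient correlation.

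**4. Two cells worked through.**

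- Baseline SD 10, slopes −0.10 to −0.20, lower correlation, b* = −0.138. Residual variance = 10.01² − 0.20² × 10² = 96.20. Excess = 0.062² × 100/96.20 = 0.40%.
- Baseline SD 16, slopes 0 to −0.30, higher correlation, b* = −0.116. Residual variance = 100.20 − 0.30² × 16² = 77.16. Excess = 0.184² × 256/77.16 = 11.2%.

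**5. All cells.** Power is Φ(4.06/(SD × √(2/97)) − 1.96).

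| Slope drift, Week 13 to Week 52 | Excess variance at Week 52 | Power forgone (points) |
|---|---|---|
| 0 | 0% | 0 |
| 0.05 | 0.1 to 0.4% | 0.1 or less |
| 0.10 | 0.4 to 1.5% | about 0.2 to 0.6 |
| 0.20 | 1.6 to 6.1% | about 0.6 to 2.3 |
| 0.30 | 3.6 to 11.2% | about 1.3 to 3.3 |

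Starting from the planning SD of 10.01, losing one point of power needs a gap between the Week 52 slope and the pooled slope of about 0.16, 0.12 or 0.10 for baseline SD 10, 13 or 16. Losing two points needs about 0.23, 0.18 or 0.14. The bounds move somewhat with the assumed correlation pattern.

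**6. Check by simulation** (MMRM by maximum likelihood, 108 per arm, 10% monotone dropout, 600 runs per scenario). Variance ratios, common slope over visit-specific slopes:

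- baseline SD 13: 1.000 for equal slopes, 1.009 for drift 0.10, about 1.03 for drift 0.20;
- baseline SD 16: 1.05 for drift 0.20.

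Mean treatment estimates from the two models agreed within about 0.02 points in every scenario.

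**7. Price of the extra term.** Three parameters (four visit slopes in place of one) against 2 × 97 = 194 evaluable patients. Taking 184 residual degrees of freedom, the t critical value moves from 1.97294 (184 df) to 1.97316 (181 df), about 0.01%.

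**The case against.** The strongest reply is that nothing here is wrong. A main-effect baseline covariate is a valid prespecified choice, and nothing in the protocol shows that the slopes differ by visit. With equal slopes the loss is exactly zero, and with a drift up to 0.10 it is at most about 1.5% of variance. That stands, and it is why the loss can only be stated as possible.

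A reader might infer that the trial is short of power because it was planned at just over 80%. The documents do not support this. The planning standard error is 10.01 × √(2/97) = 1.437. In a separate simulation with baseline SD 14, the common-slope standard errors were 1.341 for slopes −0.15 to −0.21, 1.360 for −0.05 to −0.20 and 1.283 for −0.05 to −0.35. All are below 1.437 and give about 86%, 85% and 89% power at 4.06 points. In the grid above the lowest common-slope power was 79.3%, against 81.6% with the extra term. That cell combines the widest baseline spread with a slope that changes sign. A reader might also infer bias in the Week 52 contrast; randomisation and the simulated estimates both speak against it.

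It can also be said that an SAP may complete the model. Section 11 does promise one, and 11.4.2.1 names no covariance structure. But the section itself lists the fixed effects and does not defer them, so an SAP that added the term would depart from the protocol's wording. That SAP is not at hand. The mismatch with the sensitivity ANCOVA can be read from the protocol alone; only its numerical effect needs assumed slopes.

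**Conclusion.** The point holds as a low-severity improvement. As written, the primary model has one baseline slope for four visits and tests only the last. Visit-specific slopes cannot do materially worse at Week 52 and may do somewhat better. They would also give the primary model a Week 52-specific slope, as the sensitivity ANCOVA already has.

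The gain ranges from nothing to about 11% of variance over the assumed range. It exceeds about 1.5% only in the scenarios with a drift of 0.20 or more. These figures depend on assumed baseline SDs, slopes and correlations, none of which the protocol states. It would go too far to say that the model does lose precision, or that the sample size, type I error or validity of the estimate is affected.

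**What to change.** In 11.4.2.1, add the baseline-by-time point interaction to the listed fixed effects. In 11.4.2.2, state that each secondary endpoint uses the same form with its own baseline value and its interaction with time point. Make the change, and repeat it in the SAP, before the partial database lock and unblinding described in 11.5.2.

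The cost is a short change of wording in each section and three extra fixed-effect parameters per model. The sample size need not change.

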11.4.2.2 Analyses of secondary efficacy endpoints

Secondary efficacy endpoints include:

- Change in PD-CRS (total score) from baseline to Week 52.
- Change in MDS-UPDRS Parts I+II+III from baseline to Week 52.
- Change in H&Y score from baseline to Week 52.

Secondary endpoints will be analyzed using the same MMRM model as for the primary efficacy endpoint.

11.4.2.3 Multiplicity considerations

In order to handle multiple secondary endpoints, the overall type-I error will be controlled by the use of a hierarchical approach. Statistical significance of the primary endpoint at the 2-sided 0.05 alpha level is required before drawing inferential conclusions about first secondary endpoint (refer to order of list in [Section 9.2.2](#)). Inferential conclusions about successive secondary endpoints require statistical significance of the prior one.

This fixed hierarchical approach will ensure a strong control of the overall type-I error rate at the 2-sided 0.05 level.

No further adjustments will be made for exploratory endpoints for which p-values will be provided for descriptive purpose only.

11.4.3 Analyses of safety data

Safety data will be described separately for Part 1 and Part 2 of the study, and separately for Japanese and non-Japanese patients.

Safety and tolerability in the Japanese patients from Part 1 will be compared to the non-Japanese patients.

All safety analyses will be performed on the Part 1 safety population and Part 2 safety population respectively. The summary of safety results will be presented by treatment group actually received.

The baseline value is defined generally as the last available value before randomization, within each part of the study.

For all safety data, the observation period will be divided into 3 segments within each part of the study:

- The **pretreatment period** is defined as the time between the date of the informed consent and the first administration of double-blind IMP.
- The **on-treatment period** is defined as the period from the time of first IMP administration up to 6 weeks after the last administration of the IMP.
- The **post-treatment period** starts on the day after the end of the on-treatment period.

The following definitions will be applied to laboratory parameters, vital signs, and ECGs.

- The potentially clinically significant abnormality (PCSA) values are defined as abnormal values considered medically important by the Sponsor according to predefined criteria/thresholds based on literature review and defined by the Sponsor for clinical laboratory tests, vital signs, and ECGs.
- The PCSA criteria will determine which patients had at least 1 PCSA during the on-treatment period, taking into account all evaluations performed during the on-treatment period, including unscheduled or repeated evaluations. The number of all such patients will be the numerator for the on-treatment PCSA percentage.

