Visit number	9.1 (for Japanese patients only)	10	10.1 (for Japanese patients only)	11	11.1 (for Japanese patients only)	12	12.1 (for Japanese patients only)	13	13.1 (for Japanese patients only)	14	14.1 (for Japanese patients only)	15	16
MDS-UPDRS (including H&Y)		X		X		X		X		X		X	X
PD-CRS		X		X		X		X		X		X	
MoCA		X		X		X		X		X		X	
SDMT (oral)		X		X		X		X		X		X	
TMT-A; TMT-B		X		X		X		X		X		X	
BDI-II		X		X		X		X		X		X	X
PDQ-39		X		X		X		X		X		X	
EQ-5D		X		X		X		X		X		X	
FES		X		X		X		X		X		X	
HRPQ		X		X		X		X		X		X	

Abbreviations: AE, adverse event; BDI-II: Beck Depression Inventory, second edition; CGI: Clinical Global Impression; DAT: dopamine transporters; DAT scan, ioflupane I-123 injection DaTSCAN; ECG: electrocardiogram; EQ-5D: EuroQol Five Dimensions questionnaire; FES: Falls Efficacy Scale; GL-1: glucosylceramide; H&Y: Hoehn and Yahr; HRPQ: Health-Related Productivity questionnaire; IMP, investigational medicinal product; lyso-GL-1: glucosylsphingosine; MDS-UPDRS: Movement Disorder Society-Unified Parkinson's Disease Rating Scale; MoCA: Montreal Cognitive Assessment; PD: Parkinson's disease; PD-CRS: Parkinson's Disease-Cognitive Rating Scale; PDQ-39: Parkinson's Disease Questionnaire – 39; qd, daily; SDMT: Symbol Digit Modalities Test; TMT-A: Trail-Making Test A; TMT-B: Trail Making Test B; WOCBP: women of childbearing potential.

- a* This is the study completion visit, and it should be done 8 weeks after last IMP dose; this visit also applies to early withdrawal or treatment discontinuation, if applicable. This does not apply to patients who will transition to a long-term study with GZ/SAR402671 (last visit will be week 208).
- b* Retrieve patient diary. For patients transitioning to a long-term study with GZ/SAR402671 the patient diary will be retrieved at week 208.
- c* Plasma biomarkers, including plasma GL-1 and lyso-GL-1.
- d* After 52 weeks, the patient is required to have a full ophthalmological examination at Weeks 104, 156, 208, and early withdrawal or treatment discontinuation, if applicable. Visual acuity check, slit lamp examination and funduscopy without pupil dilation are only required at Weeks 78, 130, 182, and 216 (at the 8-week follow-up [Period 4] visit). Pupil dilation/full evaluation can be performed at any time if deemed medically necessary.

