9.3 SAFETY ENDPOINTS

The observation period of safety endpoints will be divided into 3 segments:

- The **pretreatment period** is defined as the time between the date of the informed consent up to the first administration of double-blind IMP.
- The **on-treatment period** is defined as the period from the time of first IMP administration up to 6 weeks after the last administration of the IMP.
- The **post-treatment period** starts on the day after the end of the on-treatment period.

The **baseline value for safety endpoints** will be the last available value prior to the first administration of double-blind IMP.

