- Review of current medical conditions, with AE/SAE reporting (if any) (every 3 months [13 weeks] for Japanese patients only)
- Dispense IMP

At Visit 11/Week 104, Visit 13/Week 156, and Visit 15/Week 208 (ie, yearly), the following additional assessments will be performed, as listed in the study flow chart, [Section 1.3.3](#):

- Blood sampling for biomarker analysis
- Physical examination and record of body weight measurement
- 12-lead ECG
- Laboratory assessments (to be performed by the central laboratory):
 - Hematology: CBC, with differential and platelet count; coagulation profile: PT, PTT, and INR
 - Biochemistry: Sodium, potassium, chloride, calcium, ALT, AST, GGT, ALP, total and conjugated bilirubin, urea, serum creatinine, glucose, albumin, total proteins
- Urinalysis (dipstick) including glucose, protein, bilirubin, urobilinogen, pH, specific gravity, blood, ketones, nitrite, and leucocytes. Central urinalysis will be performed if any abnormality is observed in the urinalysis dipstick test.
- DAT scan
- Dispense IMP (except Visit 15/Week 208)
- Retrieve patient diary (at Visit 15/Week 208, only for patients who will transition to a long-term study with GZ/SAR402671).

Remind patient to return to the clinic for next visit.

Remind patient to not take the dose at home on the clinic visiting day, the IMP will be taken at clinic.

At Visit 15 (Week 208), patients will receive their last dose of GZ/SAR402671 at the clinic.

Visit 15 (Week 208) will be the last study visit for patients who will transition to a long-term study with GZ/SAR402671.

10.1.2.11 Eight-week follow-up visit (Period 4, end-of-study visit, Visit 16: Week 216 ±14 days)

This will be the last study visit. Patients who prematurely and permanently discontinue study medication should complete an end of treatment assessment visit (similar to Week 52/end of treatment visit for Period 2, Part 2) followed by a 8-week post-treatment follow-up visit (Visit 16). The following assessments will be performed as listed in the study flow chart, [Section 1.3.3](#), which should be done in the following order:

- BDI-II (Appendix L)
- MDS-UPDRS, including H&Y ([Appendix F](#))
- Review of concomitant medications
- Physical examination
- General neurological examination
- Visual acuity check, slit lamp examination, and fundoscopy without pupil dilation
- Vital signs: systolic and diastolic blood pressure (mm Hg), heart rate (bpm), respiratory rate (breaths/minute), and temperature (°C)

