10.4.1.3 Adverse event of special interest

An AESI is an AE (serious or nonserious) of scientific and medical concern specific to the Sponsor's product or program, for which ongoing monitoring and immediate notification by the Investigator to the Sponsor is required. Such events may require further investigation in order to characterize and understand them. Adverse event of special interest may be added, modified or removed during a study by protocol amendment.

The definition of AESI for this study are as follows:

- New or worsening lens opacities and cataracts.
- Pregnancy:
 - Pregnancy occurring in a female patient entered in the clinical trial or in a female partner of a male patient entered in the clinical trial will be recorded as an AESI with immediate notification in all cases. It will be qualified as an SAE only if it fulfills one of the seriousness criteria (see [Section 10.4.1.2](#)).
 - In the event of pregnancy in a female participant, IMP should be discontinued.
 - Follow-up of the pregnancy in a female participant or in a female partner of a male participant is mandatory until the outcome has been determined (see [Section 17 \[Appendix C\]](#)). Additional follow-up information may be requested about the baby

until at least one year after the birth of the baby, due to potential risk of abnormalities not present at birth.

- Increase in aminotransferase (ALT) (see the “Increase in ALT” flow diagram in [Section 17 \[Appendix S\]](#) of the protocol).
- Symptomatic overdose (serious or nonserious) with IMP:
 - An overdose (accidental or intentional) with the IMP is an event suspected by the Investigator or spontaneously notified by the patient (not based on systematic pills count) and defined as at least twice the intended dose within the intended therapeutic interval, adjusted according to the tested drug.

Of note, asymptomatic overdose has to be reported as a standard AE.

The circumstances (ie, accidental or intentional) should be clearly specified in the verbatim and symptoms, if any, entered on separate AE forms.

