11.4.3.1 Adverse events

Adverse event incidence tables will be presented by system organ class (sorted by internationally agreed order), high-level group term, high-level term, and preferred term sorted in alphabetical order for each treatment group, the number (n) and percentage (%) of patients experiencing an AE. Multiple occurrences of the same event in the same patient will be counted only once in the tables within a treatment period. The denominator for computation of percentages is the safety population within each treatment group.

Adverse events will be coded according to the Medical Dictionary for Regulatory Activities. The AEs will be classified into predefined standard categories according to chronological criteria:

- Pretreatment AEs: AEs that occurred or worsened during the pretreatment period;
- Treatment-emergent AEs: AEs that occurred or worsened during the on-treatment period;
- Post-treatment AEs: AEs that occurred or worsened during the post-treatment period.

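### The Part 2 on-treatment window still closes 6 weeks after last dose although the follow-up eye examination now falls at 8 weeks, so lens findings dated at that visit are nearly always classed as post-treatment

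*Protocol*

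**What the plan says.** Protocol Section 11.4.3 divides the safety observation period into three segments within each part of the study. The on-treatment segment "is defined as the period from the time of first IMP administration up to 6 weeks after the last administration of the IMP". Section 9.3 repeats the limit: "from the time of first IMP administration up to 6 weeks after the last administration of the IMP".

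Section 11.4.3.1 ties the adverse event tables to these segments: "Treatment-emergent AEs: AEs that occurred or worsened during the on-treatment period" and "Post-treatment AEs: AEs that occurred or worsened during the post-treatment period".

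For Part 2 completers, Section 10.1.2.10 fixes the last dose: "At Visit 15 (Week 208), patients will receive their last dose of GZ/SAR402671 at the clinic". The visit that follows is headed "Eight-week follow-up visit (Period 4, end-of-study visit, Visit 16: Week 216 ±14 days" in Section 10.1.2.11, and a footnote to the Section 1.3.3 schedule says "This is the study completion visit, and it should be done 8 weeks after last IMP dose". The same footnote applies the visit to early withdrawal and treatment discontinuation, and Section 10.3.4 gives patients who stop early an 8-week follow-up visit modelled on Visit 16.

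Visit 16 includes visual acuity, slit lamp and undilated funduscopy (Sections 1.3.3, 9.3.3.6 and 10.1.2.11). Section 10.4.1.3 lists "New or worsening lens opacities and cataracts" as an AESI.

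**The concern.** The lens is a target tissue in the rat toxicology described in Section 4.2.2, and the eye examinations exist because of it. The last planned look at the lens in Part 2 is the follow-up visit, and at its nominal date that visit lies two weeks beyond the end of the on-treatment period. A lens opacity is typically found by examination rather than by symptoms, so one first seen there may well carry the visit date as its onset. It would then be tabulated as post-treatment and would not enter the treatment-emergent incidence.

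The two parts are also treated differently. In Part 1 the completion visit is about 6 weeks after last dose (Section 10.1.1.9), so the same finding at that visit would nominally be treatment-emergent. One definition serves both parts but fits only the Part 1 schedule.

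**Working it through.** **Inputs (Protocol)**
- End of on-treatment period: last dose + 6 weeks = 6 × 7 = 42 days (Sections 9.3, 11.4.3).
- Last dose for completers: Visit 15, Week 208, window ±7 days (Section 10.1.2.10).
- Follow-up visit: Visit 16, Week 216, window ±14 days (Section 10.1.2.11). Both windows are anchored on Day 1 (Section 10.1.2).
- Superseded timing, from the amendment summaries: Week 214 ±7 days. It is used only to show how the mismatch arose.

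**The plan's own timing.** 208 + 8 = 216, so the Week 216 label and the 8-week description agree. Adding the 60-day screening period, 60/7 + 208 + 8 = 224.6 weeks, consistent with the stated maximum of about 224.

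**Gap from last dose to Visit 16.** Gap = (216 − 208) × 7 + a − b days, where a is the Visit 16 deviation (−14 to +14) and b the Visit 15 deviation (−7 to +7).
- Nominal: 56 days, which is 56 − 42 = 14 days past the limit.
- Last dose exactly at Week 208 (b = 0): 42 to 70 days.
- Both windows in use: 56 − 14 − 7 = 35 to 56 + 14 + 7 = 77 days.

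**Share of permitted timings inside the 42-day limit**, counting each combination of days once:

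| Case | Inside | Total | Share |
|---|---|---|---|
| Current, b = 0 | 1 | 29 | 3.4% |
| Current, both windows | 36 | 29 × 15 = 435 | 8.3% |
| Week 214 ±7 (superseded), b = 0 | 8 | 15 | 53% |
| Week 214 ±7 (superseded), both windows | 120 | 225 | 53% |

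The 36 arises because a − b must be −14 or less: 8 choices of b when a = −14, 7 when a = −13, down to 1 when a = −7, and 8 + 7 + … + 1 = 36.

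So about 92% to 97% of permitted Visit 16 timings are now outside the window. These are shares of visit timings under an assumed even spread over the windows, not shares of events. The Covid-19 extension of visit windows is left aside.

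**How far the whole window would have to move.** Under the same assumption, last dose + 8 weeks covers 52% of timings, + 10 weeks covers 94% (100% if b = 0), and + 11 weeks covers all of them.

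**Amendment 06.** Its list of changed sections includes Sections 9.3.3.3 to 9.3.3.6 but neither the period definitions in Section 9.3 nor Section 11.4.3.

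**The case against.** Six weeks is defensible as a residual-effect period. At the 31.3-hour half-life in Section 4.2.1, 42 days is 42 × 24 / 31.3 ≈ 32 half-lives. Amendment 06 lengthened the wash-out on purpose, to document the course of disease off drug, and calling that visit on-treatment sits awkwardly with that aim. Nothing in the protocol describes lens toxicity emerging after wash-out, and nothing says the follow-up visit was moved for lens safety. All of this stands, and it argues against stretching the on-treatment period for every adverse event and laboratory or vital-sign abnormality.

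The lens consequence is also bounded:
- The full dilated examinations at Weeks 52, 104, 156, 208 and at treatment discontinuation fall inside the window. For a completer, an event at stake must be absent or missed at Week 208 and then seen at an undilated examination about eight weeks later.
- Classification follows when the event occurred or worsened, and Section 10.4.2 asks the investigator for an onset date. A finding dated back to within 42 days stays treatment-emergent.

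A reader might infer that these lens findings disappear from the safety report. They do not: they are notified as AESIs within 24 hours (Section 10.4.4) and fall into the predefined post-treatment category. A reader might also infer that the placebo comparison is seriously distorted. Completers reaching Visit 16 have all been on active drug in Period 3, and patients moving to the long-term study have no Visit 16. Only patients who stop in Period 2 or do not enter Period 3 can affect the comparison.

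Section 11.5.2 leaves specific analyses up to Week 208 to the SAP, which was not available here. That does not remove the point, because the protocol itself states the classification rule, in two places. The half-life argument also concerns drug clearance, not the date on which a structural lens change is first seen.

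**Conclusion.** The point holds in a limited form. The Part 2 on-treatment window was not revisited when the follow-up visit moved, and a lens finding first seen and dated at that visit would nearly always be classed as post-treatment. The same applies to the 8-week visit after early discontinuation, nominally 14 days past the limit.

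The number of events affected cannot be given, because the protocol states no lens event rate, and it is probably small for the reasons above. The conclusion assumes that such events are dated at detection; the 92% to 97% range also assumes evenly spread visit days. It does not follow that 6 weeks is wrong as a general window, or that the whole window must be extended. The change is worth making because it concerns the compound's specific AESI and costs almost nothing.

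**What to change.** Keep the 6-week on-treatment period for other adverse events and for potentially clinically significant abnormalities. Add to Section 11.4.3, with a cross-reference in Section 9.3, wording to this effect: for Part 2, new or worsening lens opacities or cataracts first detected at the follow-up visit (Visit 16, or the 8-week visit after discontinuation) are counted in the lens AESI incidence together with treatment-emergent events, whatever the day of the visit; for patients who have started Period 3, such events are not carried back into the Period 2 comparison.

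The cost is one or two sentences, with no change to visits, examinations or treatment. The downside is that a few background lens events arising off drug will be counted.
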